## JHSPH IRB Research Plan for New Data Collection

Use this template for new data collection and if you also will analyze secondary data. Answer the questions below and for numbered sections that do not pertain to your study, retain the section numbers and bolded questions, and write "N/A". Please start typing in the gray boxes provided.

**PI Name:** [name] (JHU) & [name] (UAB)

Site PI (CIDRZ): [name]

**Study Title:** Zambia Common Elements Treatment Approach Pilot Study (ZCAP)

**IRB No.:** 8795

**PI Version No. / Date:** Version 1.2, December 5, 2018

- I. **Aims of the Study:** Describe the aims/objectives of the research and/or the project's research questions or hypotheses.

Alcohol misuse is a major unaddressed barrier to ending the HIV/AIDS epidemic. Hazardous drinking increases HIV transmission, delays antiretroviral therapy (ART) uptake, reduces adherence and retention, and increases mortality. Concerningly, alcohol consumption is increasing in sub-Saharan Africa (SSA) where 65% of persons living with HIV (PLWH) reside. In preliminary studies in Zambia, we found that: (1) 47% of male and 16% of female PLWH had hazardous use during their first year on ART, (2) among Zambians who drank hazardously, over 50% had a more severe alcohol use disorder (AUD) and/or mental health problems, and (3) over 30% reported other substance use (most commonly inhalants). Comorbid mental health or substance misuse, similar to alcohol use alone, can also significantly undermine HIV treatment.

Brief alcohol interventions (BIs), the standard of care and typically only alcohol treatment available at most SSA HIV clinics (including Zambia), can be clinically and cost effective for reducing hazardous alcohol use. However, they were not designed to treat more severe AUD or comorbid mental health/substance use problems (hereafter referred to as 'comorbidities'). When BIs are ineffective in these settings, advanced treatments are virtually non-existent. A more comprehensive alcohol treatment approach is therefore needed to reduce the impact of alcohol misuse on the HIV/AIDS response.

Cognitive-behavioral therapy (CBT) is efficacious in treating AUD among adults in high income countries; however, scalability to SSA has been limited by a lack of trained personnel and concerns over fidelity to an evidence-based treatment model. Multi-session CBT was recently shown to be feasible and efficacious among PLWH in Kenya Current approaches focus solely on alcohol and cannot address comorbidities, creating a critical gap. Our team developed Common Elements Treatment Approach (CETA), a CBT-based intervention that is delivered by lay health workers and is *transdiagnostic*, meaning a range of comorbid mental and behavioral health problems that each negatively impact HIV outcomes can be addressed. CETA was feasible and effective for treatment of a range of mental health problems in previous trials, but it has not been used among PLWH in SSA to reduce alcohol use and associated comorbidities.

We propose a Stage 1 hybrid implementation-effectiveness behavioral intervention development study to investigate CETA for alcohol reduction at HIV care settings in Zambia. Our central hypothesis is that alcohol misuse among PLWH in SSA can be addressed through a stepped care approach that includes an evidence-based BI (for

hazardous use alone) and more advanced treatment such as CETA (for hazardous use + comorbidities and for severe AUD). We will specifically test the hypotheses that (1) CETA can be feasibly delivered at HIV care settings in SSA and (2) among PLWH with hazardous use + comorbidities and/or moderate-to-severe AUD, BI+CETA will improve alcohol, mental health, and HIV outcomes compared to BI alone.

Aims include:

**Aim 1: Adapt CETA for delivery in an HIV care environment (Stage 1A).** Grounded in the Practical, Robust Implementation and Sustainability Model and informed by focus group discussions with PLWH who drink and HIV health workers, as well as interviews with key informants in the HIV and mental health system, we will adapt the CETA manual and related standard operating procedures for delivery at HIV clinics in Zambia.

**Aim 2: Pilot CETA delivery at two Zambian HIV clinics (Stage 1B).** Hypothesis 1: *BI+CETA will be clinically ( $d>0.5$ ) and statistically ( $p<.05$ ) more effective in reducing alcohol use and comorbidities than BI alone.* Hypothesis 2: *ART retention and HIV viral load (VL) will improve among recipients of BI+CETA compared to BI alone ( $p<.05$ ).* To test these hypotheses, PLWH who screen positive for hazardous alcohol use will be enrolled. Those with comorbidities and/or who meet criteria for moderate-to-severe alcohol use disorder (AUD) ( $n=160$ ) will be randomized 1:1 to receive BI+CETA or BI alone. Participants who have hazardous alcohol use but do not have a moderate-to-severe AUD and do not have mental health comorbidities will receive a BI and be assessed but not included in the pilot RCT (they will be included in the 'cohort' study). We will measure the difference in change in alcohol use and comorbidities from enrollment to 6-months follow-up and use an Ethyl glucuronide test to confirm self-reported alcohol abstinence. ART retention and VL will also be measured at enrollment and 6 months.

**Aim 3: Investigate feasibility, acceptability, and other implementation factors related to delivery of BI and CETA.** We will describe the care cascade of this approach and identify demographic, clinical, and structural correlates of uptake, engagement, and completion of the BI and CETA. We will investigate implementation factors through mixed methods interviews with study participants and health workers.

**II. Background and Rationale:** Explain why this study is being done. Summarize briefly what is already known about the issue and reference previously published research, if relevant.

- Hazardous alcohol use is common and increasing among persons living with HIV (PLWH) in sub-Saharan Africa (SSA). Alcohol is the most commonly consumed and distributed substance in SSA and prevalence of alcohol consumption is increasing rapidly. PLWH face many adversities, including low social support, trauma exposure, and stigma that increase their risk for hazardous alcohol use and they are between two and four times more likely than the general population to have an alcohol use disorder (AUD).
- Hazardous alcohol use leads to poor HIV outcomes. A recent systematic review on alcohol and HIV found that 77% of included studies reported a deleterious impact of alcohol on one or more levels of the HIV care continuum, including HIV testing, linkage and retention, ART initiation and adherence, and virologic suppression. There is growing recognition in both the US and Africa that alcohol and other substance use undermines HIV prevention and treatment programs. Alcohol impacts HIV outcomes through both behavioral and biological mechanisms, including: (1) cognitive impairment (i.e., forgetfulness), which can lead to poor ART adherence and subsequent low viral suppression; (2) increased sexual risk behaviors, which can lead to a higher risk for transmission; (3) depression, which can be a comorbidity, cause and consequence of alcohol use and is associated with decreased ART adherence and retention; (4) immunocompromise with increased susceptibility to infections; and (5) nutritional deficiencies.
- Hazardous alcohol use is a major unaddressed barrier to achieving the UNAIDS 90-90-90 goals and ending the HIV/AIDS epidemic. The majority of PLWH globally reside in SSA (approximately 25.8 million); therefore, the implementation of evidence-based interventions to address alcohol use problems in SSA has significant

potential to increase the number of PLWH receiving appropriate care and improve HIV outcomes. Alcohol reduction is particularly important for those with tuberculosis and viral hepatitis coinfection. These coinfections are leading causes of mortality among PLWH. Alcohol both increases the risk of TB and reduces treatment outcomes, while alcohol use is also linked to advanced liver fibrosis among HIV-hepatitis patients. Unfortunately, there is a substantial treatment gap for alcohol use disorders in SSA (as high as 90% in some countries) and the vast majority of PLWH who require services for alcohol use problems do not receive them. Achieving the UNAIDS 90-90-90 targets will require a more comprehensive approach to hazardous alcohol use.

- Brief interventions (BIs) are potentially effective and low-cost treatments for hazardous alcohol use. BIs typically consist of a 5-15 minute single counseling session (with possible booster sessions) administered by a primary care physician or nurse and include components such as: feedback on use and the harm drinking may be causing, norm referencing, identifying coping strategies, and motivational enhancement for changing behavior. Literature from high income countries suggests that BIs delivered in primary care settings can be both cost and clinically effective in reducing alcohol consumption for hazardous/harmful drinkers and mild AUD, including among PLWH. Evidence for the effectiveness of single-session BIs in SSA among PLWH is limited; two studies conducted in Uganda and South Africa found that alcohol consumption decreased among PLWH who received a BI but not significantly greater than a control condition.
- In addition to BIs, multi-session psychological treatments, such as cognitive behavioral therapy (CBT)-based approaches, are needed to address more severe AUD. BIs were designed to address hazardous use and other sub-threshold alcohol problems but are not intended as a stand-alone treatment for moderate-to-severe AUD or comorbidities (defined in this study as mental health or non-alcohol substance use issues). Conversely, CBT is an evidence-based psychological treatment for AUD and mental health disorders. A review of AUD interventions among PLWH found that CBT was particularly promising.
- A *transdiagnostic* CBT approach is ideal for treatment of AUD and comorbid mental health and substance use problems among PLWH. AUD is known to frequently co-occur with psychiatric disorders. Baseline data from our team's ongoing study among Zambian families affected by domestic violence suggest that hazardous alcohol use among PLWH very frequently cooccurs with depression, trauma symptoms, and other substance use (most commonly, inhalants, marijuana, and cocaine). Although the Kenya CBT study referenced above is a significant advance in SSA alcohol treatment, the paraprofessional counselors were not equipped with the skills to address comorbid conditions. This is a critical gap because mental health and other substance use problems are also associated with poor retention and adherence. In SSA, referral to a specialist for treatment of comorbidities (e.g., depression) is infeasible (Zambia for example has only 5 qualified psychiatrists, none outside Lusaka). Therefore, an innovative common elements, or transdiagnostic, treatment approach is a preferred strategy. In a transdiagnostic approach, therapists are trained in common elements that exist across a number of evidence-based mental health treatments and are provided with the knowledge and skills to manage a wide range of mental and behavioral health problems and severities, thereby removing the 'silos' that exist within mental health care. Studies have indicated the effectiveness of transdiagnostic treatments in reducing common and co-occurring mental and behavioral health problems that each can impact HIV outcomes, however they have not yet been tested in SSA clinic settings among PLWH for alcohol reduction.
- A stepped care approach to the treatment of hazardous alcohol use and AUD within SSA HIV care settings has potential to efficiently provide targeted, evidence-based interventions. A stepped care approach, which has been utilized for alcohol use, mental health, and management of other chronic diseases in high income settings, involves the provision of interventions that range in intensity--and resources required--commensurate with symptom severity. Referral is made to the lowest-intensity level intervention

appropriate for presenting symptoms. If treatment fails, the patient is referred to a higher 'step' intervention. Applied to alcohol treatments in HIV care, this could involve a lower-intensity intervention, such as BI, for patients who present with hazardous use or sub-threshold AUD, and a higher-intensity intervention, such as transdiagnostic CBT, for patients who present with moderate-to-severe AUD or comorbidities. A third step may include referral to a specialist and consideration of pharmacotherapy, when available. Although recommended by the World Health Organization (WHO) to improve reach and efficient delivery of interventions, we are not aware of studies investigating a stepped care approach for the treatment of alcohol use problems in SSA.

- In summary, the scientific premise of this proposal is that alcohol use in Zambia and SSA is increasing and has a significant negative impact on HIV outcomes, yet treatments are severely lacking. Some hazardous drinkers may respond to BIs; however, HIV clinics need access to more advanced treatments for moderate-to-severe AUD and comorbidities. In this project we will adapt, integrate, and pilot a transdiagnostic CBT-based treatment (CETA) within HIV care in Zambia and test its preliminary effectiveness at addressing these higher step problems. This project will lay the foundation for a stepped care approach to alcohol reduction that can be tested in a larger follow-up study.

### III. Study Design:

- A. Provide an overview of your study design and methods. The study design must relate to your stated aims/objectives. Details will be requested later. If your study also involves analysis of existing data, please complete Section XI, "Secondary Data Analysis of Existing Data" in the last part of this research plan. If your study ONLY involves analysis of existing data, please use the research plan template for secondary data analysis (JHSPH IRB Research Plan for Secondary Data Analysis of Existing Data/Specimens).

Following the NIH Stage Model for Behavioral Intervention Development, we will conduct a Stage 1 study in two phases: (1) adaptation and refinement of an existing behavioral intervention in new and 'real-world' settings (Stage 1A) and (2) pilot testing of the adapted intervention to assess feasibility and preliminary effectiveness (Stage 1B). In Stage 1A (Aim 1), we will adapt CETA for use in HIV clinics through formative research, including a review of national HIV care protocols and focus groups with PLWH who drink and HIV clinic staff at the study sites. We will also conduct key informant interviews with policy-level officials. We will adapt and tailor the CETA manual for use with PLWH, with input from stakeholders. In Stage 1B (Aims 2/3), we will conduct a pilot RCT of BI+CETA compared to BI alone for PLWH with moderate-to-severe AUD and/or hazardous use with comorbidities. We will collect mixed methods implementation data and clinical outcomes data on alcohol, comorbidities, and HIV (ART retention and VL collected through routine care).

- B. Provide a sample size and a justification as to how you arrived at that number. If you use screening procedures to arrive at a final sample a table may be helpful.

The total sample size for the study is 400. This includes a maximum of 80 participants in Stage 1A and 320 in Stage 1B.

Stage 1A: There are no formal sample size calculation for this qualitative, formative stage of the study, in which we will conduct focus groups and in-depth interviews. We will conduct 4 focus group discussions (FGDs) with PLWH who use alcohol. Each group will have a maximum number of participants of 8. Therefore, the maximum

number of PLWH participants in Stage 1A will be n=32. Additionally, we will conduct 4 FGDs with health workers at our study clinics. These FGDs will also have a maximum number of 8 participants per group, thus the maximum number of healthcare worker participants will be n=32. Finally, we will conduct up to 16 key informant interviews with policy officials and relevant program leaders.

Stage 1B: This stage will enroll n=320 participant who have hazardous alcohol use: n=160 will formally be enrolled in the RCT (participants who meet criteria for a moderate-to-severe AUD or have hazardous alcohol use plus comorbidities) and n=160 who will not be enrolled in the RCT but will receive the BI and will be tracked for follow-up in a cohort study (participants with hazardous use but do not have a moderate-to-severe AUD and have no comorbidities).

The primary endpoint of the pilot RCT is the difference in change in AUDIT score from baseline to 6-month follow-up between BI+CETA and BI alone (see assessments section below). We believe that an effect size of CETA  $\geq 0.5$  would be clinically significant and justify further investigation in a subsequent latter Stage trial. Further assuming  $\alpha=0.05$  and  $\beta=80\%$ , we will require a total sample size of 128 (n=64 per arm). To account for possible loss-to-follow-up/drop-out of 20% based on our previous studies with HIV-affected populations in Zambia, we will inflate the sample size to 160 (n=80 per arm). Based on Preliminary Studies, we anticipate that 20% of female and 40% of male patients at the study sites will report hazardous drinking and that 50% of hazardous drinkers will qualify for the RCT. Therefore, we expect to enroll n=320 hazardous drinkers to reach the RCT target sample size. There is no sample size calculation for cohort study participant; however, the anticipated sample of n=160 should be sufficient to detect even a small within-group change in outcomes after receipt of BI.

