Study Phase	Activity	Year 1				Year 2				Year 3			
		Q 1	Q 2	Q 3	Q 4	Q 1	Q 2	Q 3	Q 4	Q 1	Q 2	Q 3	Q 4
Planning	Study protocol finalization and ethical approval												
	Staff hiring and site preparation												
	Training of qualitative data staff												
Stage 1A	Focus groups and key informant interviews												
	Adaptation of CETA for PLWH												
	Development of CETA protocol in HIV care based on Stage 1A												
	CETA/mhGAP-IG trainings, assessor trainings, M&E trainings												
Stage 1B	CETA pilot cases												
	Recruitment, consent, screening and baseline assessments (ACASI, HIV)												
	Interventions active												
	Post-treatment assessments (ACASI, UEtG)												
	6-month outcomes assessment (ACASI, UEtG, HIV outcomes via chart review)												
Analysis, dissemination, and next steps	Implementation data collection (PLWH, clinic staff, policy officials)												
	Data analysis												
	Report/manuscript writing and dissemination at conferences												
	Preparation and submission of follow-up R01												

- Provide a brief data analysis plan and a description of variables to be derived.

*Analysis of treatment uptake and completion.* We will estimate a logit model with a binary outcome (1=completer; 0=non-completer) to assess predictors of treatment completion. Predictors will be demographic (e.g., sex, age), clinical (e.g., symptom severity), and structural (e.g., distance from clinic) level factors.

*Analysis of ACASI outcome data.* Analyses will be intent-to-treat. AUDIT score, along with other continuous secondary outcomes (Past 30-Day TLFB [% days drinking and mean drinks per day], CES-D, HTQ, ASSIST scores) will be modelled with linear mixed models. Fixed effects will include treatment arm (0=BI; 1=BI+CETA), time (0=Baseline; 1=6-months post-baseline), and interaction terms between treatment arm

and time. This will allow estimation of the mean difference in change in score between arms and 95% confidence intervals. Cohen's D will be calculated to estimate effect size. Covariates will be included if they differ meaningfully at baseline or predict significant change in the outcome. For dichotomous outcomes or non-normally distributed continuous outcomes, generalized linear mixed effects models will be estimated. Paired t-tests will be used to assess within group change among the non-Pilot RCT hazardous drinkers.

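### Does writing beta as 80%, or pairing d>0.5 with p<.05 in Hypothesis 1, undermine the sample size of 128?

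*Combined protocol and SAP*

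**What the plan says.** Section III.B names one primary endpoint: "The primary endpoint of the pilot RCT is the difference in change in AUDIT score from baseline to 6-month follow-up", compared between BI+CETA and BI alone. It then says that an effect size of at least 0.5 "would be clinically significant and justify further investigation in a subsequent latter Stage trial", adds alpha and the 80% figure as further assumptions, and reaches the evaluable sample: "\beta=80\%$ , we will require a total sample size of 128 (n=64 per arm". For 20% loss to follow-up this is raised to 160, or 80 per arm. The section does not say whether the test is one- or two-sided, or which standard deviation defines the effect size.

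Section I, Aim 2, words Hypothesis 1 as: "BI+CETA will be clinically ( $d>0.5$ ) and statistically ( $p<.05$ ) more effective in reducing alcohol use and comorbidities than BI alone".

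The data analysis plan in Section V (analysis of ACASI outcome data) fits a linear mixed model with an arm-by-time interaction, which is to give "estimation of the mean difference in change in score between arms and 95% confidence intervals". Of Cohen's measure it says only that it "D will be calculated to estimate effect size". Section X.C plans no interim analyses.

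**The concern.** Two things catch the eye.

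First, beta is the chance of missing a true effect. A trial planned with beta of 80% would miss a true effect of 0.5 four times in five. An error in the sentence that justifies the sample size raises the question whether the sample size itself is wrong.

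Second, Hypothesis 1 joins a clinical and a statistical condition. Since p<.05 is a condition on the observed result, d>0.5 can be read the same way. The 80% in Section III.B covers p<.05 only. If both conditions had to be met, the trial's chance of success at its own planning effect would be well below 80%. A result between the two cut-offs would also have no stated interpretation. For example, an observed d of 0.40 with 64 per arm gives p=0.025 and a 95% interval of 0.05 to 0.75.

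**Working it through.** **Inputs.** From Section III.B: effect d=0.5, alpha 0.05, the 80% figure, 64 per arm evaluable, 20% loss, 80 per arm randomised. From Aim 2: 1:1 allocation, d>0.5 and p<.05. Assumed: a two-sided test, and (in steps 1 to 3) d expressed in units of the SD of change.

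**1. The plan's own figure.** The normal approximation for the number per arm is 2(z_0.975 + z_0.80)²/d² = 2(1.960 + 0.842)²/0.25, which rounds up to 63. The two-sample t-test gives 63.77, so 64 per arm and 128 in total. Power at 64 per arm is 0.801. Allowing for loss, 128/0.8 = 160. The alternatives do not fit:

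| Reading of the 80% figure | n per arm (t-test) |
|---|---|
| Power 80%, two-sided | 64 |
| Power 80%, one-sided | 51 |
| Beta 80% (power 20%), two-sided | 11 |

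Only the first row reproduces the plan, so both the intended power and the sidedness can be recovered from the stated numbers.

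**2. Where significance starts.** With 64 per arm, the smallest significant observed d is t_0.975,126 × √(2/64) = 1.979 × 0.1768 = 0.350.

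**3. If d>0.5 were a cut-off on the estimate.** The chance of meeting both conditions is the upper tail of the noncentral t with 126 degrees of freedom and noncentrality d√(n/2), beyond the larger of the t critical value and 0.5√(n/2). At n=64 these are 1.979 and 0.5 × √32 = 2.828, so the cut-off on d decides.

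| True d | p<.05 alone | Both conditions | p<.05 but observed d of 0.5 or less |
|---|---|---|---|
| 0.50 | 80% | 50% | 30% |
| 0.60 | 92% | 71% | 21% |
| 0.65 | 95% | 80% | 15% |

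At a true d of 0.5 the joint figure does not depend on size once n reaches 32 per arm: 0.503 at 32, 0.502 at 64, 0.502 at 80, 0.501 at 1000. The 50% is therefore a general property of setting the cut-off equal to the true effect, where the estimate falls on either side about equally often. It reveals nothing about the adequacy of 128.

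**4. Which reading the text supports.** In Section III.B the 0.5 comes first, alpha and power are added to it as further assumptions, and the sample size follows from all three. That is the role of a planning effect. The analysis plan attaches no decision to Cohen's d, and no section gives a rule for proceeding or stopping based on it. With d>0.5 as the effect the trial is designed to find, the 80% in step 1 is the right power.

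**5. The unstated SD.** If d were standardised by the baseline SD, the SD of change would be √(2(1 − r)) baseline SDs, where r is the baseline-to-follow-up correlation. The plan gives no r; assumed values with 64 per arm give:

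| Assumed r | Smallest significant d | Power for p<.05 at d=0.5 | Both conditions at d=0.65 |
|---|---|---|---|
| 0.3 | 0.41 | 66% | 76% |
| 0.5 | 0.35 | 80% | 80% |
| 0.7 | 0.27 | 95% | 86% |

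So the figures in steps 2 and 3 hold for the SD of change (or equivalently r=0.5). The documents give no basis for prescribing either SD.

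**The case for a change.** The strongest case for a change is that Hypothesis 1 puts its two conditions in parallel, and one of them can only refer to observed data. The pilot is meant to lay the ground for a larger trial, so an observed effect between 0.35 and 0.5 is a realistic outcome. Without a stated reading, the team could choose after seeing the data whether such a result supports the hypothesis. A sentence of clarification would cost nothing, and the trial does have a formal hypothesis and a power calculation, so calling it a pilot is not an answer.

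Part of this stands. The symbol is wrong, the sidedness and the SD behind d are not written down, and the wording of Hypothesis 1 permits the cut-off reading. But nothing in the plan depends on which side of 0.5 the estimate falls. The mean difference in AUDIT change will be reported with its 95% confidence interval, so a reader who sees d=0.40 and p=0.025 will also see how imprecise the effect is. A separate interval for d would add little. The 80% against 50% contrast is also taken at a true d of exactly 0.5, a value that does not itself satisfy d>0.5.

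**Conclusion.** No change to the plan follows. The label on the 80% is a clerical slip: 64 per arm, 128 evaluable and 160 randomised are all correct for 80% power, two-sided, at d=0.5, and a reader can confirm this from the stated numbers. The role of d>0.5 is a gap that analysts would fill sensibly from Section III.B, where 0.5 is the planning effect and the 80% is the chance of p<.05 on AUDIT change.

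The drop to about 50% arises only if d>0.5 is an observed cut-off, which no section states. Even then a larger sample would not raise it at a true d of 0.5. The conclusion assumes a two-sided test, 64 evaluable per arm and, for the 80% itself, d in units of the SD of change. If the protocol is amended for other reasons, the authors may wish to correct the symbol and say which SD defines d, but the sample size, the analysis and the interpretation of the trial do not depend on it.
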